7.1.1.4.2 Concomitant Medications

The investigator or qualified designee will record medication, if any, taken by the subject during the trial. All medications related to reportable SAEs should be recorded as defined in Section 7.2.

7.1.1.5 Disease Details and Treatments

7.1.1.5.1 Disease Details

The investigator or qualified designee will obtain prior and current details regarding disease status.

7.1.1.5.2 Prior Treatment Details

The investigator or qualified designee will review all prior cancer treatments including systemic treatments, radiation and surgeries.

Product: Pembrolizumab

Protocol/Amendment No.: 2016-0343 Amendment 2

41

7.1.1.5.3 Subsequent Anti-Cancer Therapy Status

The investigator or qualified designee will review all new anti-neoplastic therapy initiated after the last dose of trial treatment. If a subject initiates a new anti-cancer therapy within 30 days after the last dose of trial treatment, the 30 day Safety Follow-up visit must occur before the first dose of the new therapy. Once new anti-cancer therapy has been initiated the subject will move into survival follow-up.

7.1.1.6 Assignment of Screening Number.

Per institutional guidelines

7.1.1.7 Assignment of Randomization Number N/A

7.1.1.8 Trial Compliance (Medication/Diet/Activity/Other)

Per institutional guidelines.

7.1.2 Clinical Procedures/Assessments

7.1.2.1 Adverse Event (AE) Monitoring

The investigator or qualified designee will assess each subject to evaluate for potential new or worsening AEs as specified in the Trial Flow Chart and more frequently if clinically indicated. Adverse experiences will be graded and recorded throughout the study and during the follow-up period according to NCI CTCAE Version 4.0 (see Appendix E in PDOL). Toxicities will be characterized in terms regarding seriousness, causality, toxicity grading, and action taken with regard to trial treatment.

Please refer to section 7.2 for detailed information regarding the assessment and recording of AEs.

7.1.2.2 Full Physical Exam

The investigator or qualified designee will perform a complete physical exam during the screening period. Clinically significant abnormal findings should be recorded as medical history.

7.1.2.3 Directed Physical Exam

For cycles that do not require a full physical exam per the Trial Flow Chart, the investigator or qualified designee will perform a directed physical exam as clinically indicated prior to trial treatment administration.

Product: Pembrolizumab

Protocol/Amendment No.: 2016-0343 Amendment 2

7.1.2.4 Vital Signs

The investigator or qualified designee will take vital signs at screening, prior to the administration of each dose of trial treatment and at treatment discontinuation as specified in the Trial Flow Chart (Section 6.0). Vital signs should include temperature, pulse, respiratory rate, weight and blood pressure. Height will be measured at screening only.

7.1.2.5 Eastern Cooperative Oncology Group (ECOG) Performance Scale

The investigator or qualified designee will assess ECOG status (see Appendix D in PDOL) at screening, prior to the administration of each dose of trial treatment and discontinuation of trial treatment as specified in the Trial Flow Chart.

7.1.2.6 Tumor Imaging and Assessment of Disease

There is no indication for imaging studies for patients with MDS. Bone marrow specimens to evaluate response and when agreed for exploratory correlative studies will be performed at baseline and on after cycle 1, cycle 3 and then every 3 months. Bone marrow studies will include aspirate, biopsy (when indicated). Samples will be obtained also for cytogenetic and molecular analysis following institutional guidelines.

7.1.2.7 Tumor Tissue Collection and Correlative Studies Blood Sampling

Patients will be consented to institutional consents for sample acquisition and analysis as described in the text and pertinent tables.

7.1.3 Laboratory Procedures/Assessments

Details regarding specific laboratory procedures/assessments to be performed in this trial are provided below in Table 6.

Table 6 Laboratory Tests

Hematology	Chemistry	Urinalysis	Other
Hematocrit	Albumin	Blood	Serum β -human chorionic gonadotropin† (β -hCG)†
Hemoglobin	Alkaline phosphatase	Glucose	PT (INR)
Platelet count	Alanine aminotransferase (ALT)	Protein	aPTT
WBC (total and differential)	Aspartate aminotransferase (AST)	Specific gravity	
Red Blood Cell Count	Lactate dehydrogenase (LDH)	Microscopic exam (If abnormal)	Total triiodothyronine (T3)
Absolute Neutrophil Count	Carbon Dioxide ‡ (CO_2 or bicarbonate)	results are noted	Free tyroxine (T4)
Absolute Lymphocyte Count	Uric Acid	Urine pregnancy test †	Thyroid stimulating hormone (TSH)
	Calcium		
	Chloride		
	Glucose		Blood for correlative studies
	Phosphorus		
	Potassium		
	Sodium		
	Magnesium		
	Total Bilirubin		
	Direct Bilirubin (If total bilirubin is elevated above the upper limit of normal)		
	Total protein		
	Blood Urea Nitrogen		
	Creatinine		

† Perform on women of childbearing potential only. If urine pregnancy results cannot be confirmed as negative, a serum pregnancy test will be required.

‡ If considered standard of care in your region.

Product: Pembrolizumab
Protocol/Amendment No.: 2016-0343 Amendment 2

Product: Pembrolizumab
Protocol/Amendment No.: 2016-0343 Amendment 3.4

7.1.4 Other Procedures

7.1.4.1 Withdrawal/Discontinuation

When a subject discontinues/withdraws prior to trial completion, all applicable activities scheduled for the final trial visit should be performed at the time of discontinuation. Any adverse events which are present at the time of discontinuation/withdrawal should be followed in accordance with the safety requirements outlined in Section 7.2 - Assessing and Recording Adverse Events. Subjects who a) attain a CR or b) complete 24 months of treatment with pembrolizumab may discontinue treatment. After discontinuing treatment following assessment of CR, these subjects should return to the site for a Safety Follow-up Visit (described in Section 7.1.5.3.1) and then proceed to the Follow-Up Period of the study (described in Section 7.1.5.4).

7.1.4.2 Blinding/Unblinding N/A

7.1.5 Visit Requirements

Visit requirements are outlined in Section 6.0 - Trial Flow Chart. Specific procedure-related details are provided above in Section 7.1 - Trial Procedures.

7.1.5.1 Screening

Per table 6.1

7.1.5.1.1 Screening Period

Per table 6.1

7.1.5.2 Treatment Period

Per table 6.1

7.1.5.3 Post-Treatment Visits

Per table 6.1

7.1.5.3.1 Safety Follow-Up Visit

The mandatory Safety Follow-Up Visit should be conducted approximately 30 days after the last dose of trial treatment or before the initiation of a new anti-cancer treatment, whichever comes first. All AEs that occur prior to the Safety Follow-Up Visit should be recorded. Subjects with an AE of Grade > 1 will be followed until the resolution of the AE to Grade 0-1 or until the beginning of a new anti-neoplastic therapy, whichever occurs first. SAEs that occur within 90 days of the end of treatment or before initiation of a new anti-cancer treatment should also be followed and recorded.

7.1.5.4 Follow-up Visits

Subjects who discontinue trial treatment for a reason other than disease progression will move into the Follow-Up Phase and should be assessed about every 6-8 weeks (\pm 7 days) as clinically indicated to monitor disease status. Every effort should be made to collect information regarding disease status until the start of new anti-neoplastic therapy, disease progression, death, end of the study or if the subject begins retreatment with pembrolizumab. Information regarding post-study anti-neoplastic treatment will be collected if new treatment is initiated.

Survival Follow-up

Once a subject experiences confirmed disease progression or starts a new anti-cancer therapy, the subject moves into the survival follow-up phase and should be contacted by telephone every 12 weeks to assess for survival status until death, withdrawal of consent, or the end of the study, whichever occurs first.

7.2 Assessing and Recording Adverse Events

An adverse event is defined as any untoward medical occurrence in a patient or clinical investigation subject administered a pharmaceutical product and which does not necessarily have to have a causal relationship with this treatment. An adverse event can therefore be any unfavorable and unintended sign (including an abnormal laboratory finding, for example), symptom, or disease temporally associated with the use of a medicinal product or protocol-specified procedure, whether or not considered related to the medicinal product or protocol-specified procedure. Any worsening (i.e., any clinically significant adverse change in frequency and/or intensity) of a preexisting condition that is temporally associated with the use of the Merck's product, is also an adverse event.

Merck product includes any pharmaceutical product, biological product, device, diagnostic agent or protocol-specified procedure, whether investigational (including placebo or active comparator medication) or marketed, manufactured by, licensed by, provided by or distributed by Merck for human use.

Adverse events may occur during the course of the use of Merck product in clinical trials or within the follow-up period specified by the protocol, or prescribed in clinical practice, from overdose (whether accidental or intentional), from abuse and from withdrawal.

Adverse events may also occur in screened subjects during any pre-allocation baseline period as a result of a protocol-specified intervention, including washout or discontinuation of usual therapy, diet, placebo treatment or a procedure.

Progression of the cancer under study is not considered an adverse event unless it is considered to be drug related by the investigator.

Product: Pembrolizumab

Protocol/Amendment No.: 2016-0343 Amendment 3.4

All adverse events will be recorded in PDMS/CORe from the time the consent form is signed through 30 days following cessation of treatment and at each examination.

- The protocol specific data will be entered into PDMS/CORe, the electronic case report.
- The Investigator or physician designee is responsible for providing source documentation and assigning attribution for all AEs.

7.2.1 Definition of an Overdose for This Protocol and Reporting of Overdose to the Sponsor and to Merck

For purposes of this trial, an overdose of pembrolizumab will be defined as any dose of 1,000 mg or greater (≥ 5 times the indicated dose). No specific information is available on the treatment of overdose of pembrolizumab. Appropriate supportive treatment should be provided if clinically indicated. In the event of overdose, the subject should be observed closely for signs of toxicity. Appropriate supportive treatment should be provided if clinically indicated.

If an adverse event(s) is associated with (“results from”) the overdose of a Merck product, the adverse event(s) is reported as a serious adverse event, even if no other seriousness criteria are met.

All reports of overdose with and without an adverse event must be reported within 24 hours to the Sponsor and within 2 working days hours to Merck Global Safety. (Attn: Worldwide Product Safety; [contact])

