5.2.1.2 Dose Modification of MK3475

Adverse events (both non-serious and serious) associated with pembrolizumab exposure may represent an immunologic etiology. These adverse events may occur shortly after the first dose or several months after the last dose of treatment. Pembrolizumab must be withheld for drug-related toxicities and severe or life-threatening AEs as per Table 3 below. See Section 5.6.1 for supportive care guidelines, including use of corticosteroids.

Table 3. Dose Modification Guidelines for Drug-Related Adverse Events

Toxicity	Hold Treatment For Grade	Timing for Restarting Treatment	Discontinue Subject
Diarrhea/ Colitis	2-3	Toxicity resolves to Grade 0-1	Toxicity does not resolve within 12 weeks of last dose or inability to reduce corticosteroid to 10 mg or less of prednisone or equivalent per day within 12 weeks.

Product: Pembrolizumab

Protocol/Amendment No.: 2016-0343 Amendment 3.4

Toxicity	Hold Treatment For Grade	Timing for Restarting Treatment	Discontinue Subject
	4	Permanently discontinue	Permanently discontinue
AST, ALT, or Increased Bilirubin	2	Toxicity resolves to Grade 0-1	Toxicity does not resolve within 12 weeks of last dose.
	3-4	Permanently discontinue (see exception below) ¹	Permanently discontinue
Type 1 diabetes mellitus (if new onset) or Hyperglycemia	T1DM or 3-4	Hold pembrolizumab for new onset Type 1 diabetes mellitus or Grade 3-4 hyperglycemia associated with evidence of beta cell failure.	Resume pembrolizumab when patients are clinically and metabolically stable.
Hypophysitis	2-3	Toxicity resolves to Grade 0-1	Toxicity does not resolve within 12 weeks of last dose or inability to reduce corticosteroid to 10 mg or less of prednisone or equivalent per day within 12 weeks.
	4	Permanently discontinue NOTE: Grade 4 hypophysitis does not require stopping therapy with pembrolizumab as long as the pituitary hormones are replaced.	Permanently discontinue NOTE: Grade 4 hypophysitis does not require stopping therapy with pembrolizumab as long as the pituitary hormones are replaced.
Hyperthyroidism	3	Toxicity resolves to Grade 0-1	Toxicity does not resolve within 12 weeks of last dose or inability to reduce corticosteroid to 10 mg or less of prednisone or equivalent per day within 12 weeks.
	4	Permanently discontinue	Permanently discontinue

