The End of Treatment and Follow-up visit procedures are listed in Section 6 (Protocol Flow Chart) and Section 7.1.5 (Visit Requirements). After the end of treatment, each subject will be followed for 30 days for adverse event monitoring (serious adverse events will be collected for 90 days after the end of treatment as described in Section 7.2.3.1). Subjects who discontinue for reasons other than progressive disease will have post-treatment follow-up for disease status until disease progression, initiating a non-study cancer treatment, withdrawing consent or becoming lost to follow-up. After documented disease progression each subject will be followed by telephone, every 12 weeks, for overall survival until death, withdrawal of consent, or the end of the study, whichever occurs first.

Product: Pembrolizumab

Protocol/Amendment No.: 2016-0343 Amendment 3.4

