- **Note:** In addition to the above criteria, adverse events meeting either of the below criteria, although not serious per ICH definition, are reportable to the Merck in the same timeframe as SAEs to meet certain local requirements. Therefore, these events are considered serious by Merck for collection purposes.
 - Is a new cancer (that is not a condition of the study);
 - Is associated with an overdose.

Refer to Table 6 for additional details regarding each of the above criteria.

For the time period beginning when the consent form is signed until treatment allocation/randomization, any serious adverse event, or follow up to a serious adverse event, including death due to any cause, that occurs to any subject must be reported within 24 hours to the Sponsor and within 2 working days to Merck Global Safety if it causes the subject to be excluded from the trial, or is the result of a protocol-specified intervention, including but not limited to washout or discontinuation of usual therapy, diet, placebo treatment or a procedure.

For the time period beginning at treatment allocation/randomization through 90 days following cessation of treatment, or 30 days following cessation of treatment if the subject initiates new anticancer therapy, whichever is earlier, any serious adverse event, or follow up to a serious adverse event, including death due to any cause whether or not related to the Merck product, must be reported within 24 hours to the Sponsor and within 2 working days to Merck Global Safety.

Additionally, any serious adverse event, considered by an investigator who is a qualified physician to be related to Merck product that is brought to the attention of the investigator at any time following consent through the end of the specified safety follow-up period specified in the paragraph above, or at any time outside of the time period specified in the previous paragraph also must be reported immediately to the Sponsor and to Merck Global Safety.

All subjects with serious adverse events must be followed up for outcome.

SAE reports and any other relevant safety information are to be forwarded to the Merck Global Safety [contact]

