7.2.3.2 Events of Clinical Interest

Selected non-serious and serious adverse events are also known as Events of Clinical Interest (ECI) and must be reported within 24 hours to the Sponsor and within 2 working days to Merck Global Safety. (Attn: Worldwide Product Safety; [contact]).

For the time period beginning when the consent form is signed until treatment allocation/randomization, any ECI, or follow up to an ECI, that occurs to any subject must be reported within 24 hours to the Sponsor and within 2 working days to Merck Global Safety if it causes the subject to be excluded from the trial, or is the result of a protocol-specified intervention, including but not limited to washout or discontinuation of usual therapy, diet, placebo treatment or a procedure.

For the time period beginning at treatment allocation/randomization through 90 days following cessation of treatment, or 30 days following cessation of treatment if the subject initiates new anticancer therapy, whichever is earlier, any ECI, or follow up to an ECI, whether or not related to Merck product, must be reported within 24 hours to the Sponsor and within 24 hours to Merck Global Safety.

Events of clinical interest for this trial include:

1. an overdose of Merck product, as defined in Section 7.2.1 - Definition of an Overdose for This Protocol and Reporting of Overdose to the Sponsor, that is not associated with clinical symptoms or abnormal laboratory results.
2. an elevated AST or ALT lab value that is greater than or equal to 3X the upper limit of normal and an elevated total bilirubin lab value that is greater than or equal to 2X the upper limit of normal and, at the same time, an alkaline phosphatase lab value that is less than 2X the upper limit of normal, as determined by way of protocol-specified laboratory testing or unscheduled laboratory testing.*

***Note:** These criteria are based upon available regulatory guidance documents. The purpose of the criteria is to specify a threshold of abnormal hepatic tests that may require an additional evaluation for an underlying etiology.

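### New non-serious immune events after about day 30 off treatment can go unrecorded, and two SAE cut-offs conflict for patients starting new therapy within 90 days

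*Combined protocol and SAP*

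**What the plan says.** **Timing of the risk.** Section 5.2.1.2 introduces pembrolizumab adverse events, serious and non-serious alike, as possibly immunologic, and says: "These adverse events may occur shortly after the first dose or several months after the last dose of treatment".

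**General AE capture.** Section 5.8 says that after the end of treatment "each subject will be followed for 30 days for adverse event monitoring". Section 7.1.5.3.1 has AEs recorded up to the Safety Follow-Up Visit, which falls at about day 30, or before new anti-cancer treatment if that comes first. Section 7.2 says: "All adverse events will be recorded in PDMS/CORe from the time the consent form is signed through 30 days following cessation of treatment". That sentence does not end there; its close reads "through 30 days following cessation of treatment and at each examination". Section 7.1.2.1 has AEs graded and recorded during the study and the follow-up period, without a day limit.

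**Longer routes.** Section 7.2.3.2 allows non-serious events to be reported to day 90 (day 30 if new therapy starts) as events of clinical interest. Its list, opened by "Events of clinical interest for this trial include", has two entries: overdose without symptoms or abnormal laboratory results, and a combined transaminase, bilirubin and alkaline phosphatase threshold. Section 7.2.3.1 requires SAEs judged related to the Merck product to be reported whenever they come to light.

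**SAE window.**
- Section 5.8: "serious adverse events will be collected for 90 days after the end of treatment as described in Section 7.2.3.1".
- Section 7.1.5.3.1: "SAEs that occur within 90 days of the end of treatment or before initiation of a new anti-cancer treatment".
- Section 7.2.3.1: "90 days following cessation of treatment, or 30 days following cessation of treatment if the subject initiates new anticancer therapy, whichever is earlier".

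**The concern.** Safety is the first primary objective (section 3.1), and section 8.1 stops a cohort on therapy-related non-hematological grade 3/4 toxicity. The protocol expects part of pembrolizumab's immune toxicity to appear after treatment ends, yet the sections that give a day limit close general AE recording at about day 30. If no other route catches a later event, it reaches neither the safety tables nor, when it is a related grade 3/4 event, the counts used with Tables 8 and 11.

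The SAE conflict affects a foreseeable group, namely patients who stop and soon start something else. Section 5.2 lists progression and possible transplant among the reasons to stop, although the documents do not say whether transplant counts as new anti-cancer therapy. For these patients, two careful readers could close the SAE window on different days.

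**Working it through.** No figure in the plan sizes this gap, so the main check sets the sections side by side.

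**1. Which route catches an immune event that begins after day 30?**

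| Event beginning after day 30 | Route | Recorded? |
|---|---|---|
| Serious, judged related to the Merck product | 7.2.3.1, no time limit | Yes |
| Serious, judged unrelated | 7.2.3.1 or 7.1.5.3.1 window | To day 90 without new therapy; otherwise depends on the section followed |
| Non-serious, meets the combined liver-test threshold | 7.2.3.2 | To day 90, or day 30 if new therapy starts |
| Non-serious pneumonitis, colitis, hypophysitis, nephritis, thyroid disease or type 1 diabetes | None with a stated duty and day limit | Unclear |

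The last row contains event types that Table 3 and section 5.6.1 single out. Sections 7.1.2.1 and 7.2 have looser wording that could reach them, but section 7.1.5.4 gives later visits the purpose of monitoring disease status and the 12-weekly calls that of survival status. Neither contact is assigned AE questioning.

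**2. Last SAE day, by the day *d* on which new therapy starts.** Section 7.1.5.3.1 is read as min(90, *d*). Section 7.2.3.1 is read as 30 if *d* is 90 or less, and otherwise 90.

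| New therapy starts | 7.1.5.3.1 | 7.2.3.1 |
|---|---|---|
| Not by day 90 | 90 | 90 |
| Day 10 | 10 | 30 |
| Day 30 | 30 | 30 |
| Day 45 | 45 | 30 |
| Day 60 | 60 | 30 |

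Section 7.1.5.3.1 is shorter before day 30 and longer from day 31 to day 90. For a start on day 45, section 7.2.3.1 closes the window at a day that has already passed.

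**3. How sensitive is the stopping rule to one unrecorded patient?** The inputs are the beta(0.6, 1.4) prior, the 0.30 limit and the 0.95 threshold in section 8.1. With x toxicities in n patients the posterior is beta(0.6 + x, 1.4 + n − x). The resulting boundaries of 4/5, 6/10 and 8/15 reproduce Tables 8 and 11.

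- 5/10: beta(5.6, 6.4), P(toxicity > 0.30) = 0.880, continue.
- 6/10: beta(6.6, 5.4), P = 0.962, stop.
- 7/15: beta(7.6, 9.4), P = 0.893, continue.
- 8/15: beta(8.6, 8.4), P = 0.960, stop.

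**4. Illustration only.** The documents give no share of late events. Assume that a fraction u of qualifying toxicities is missed at every look, so the recorded rate is the true rate × (1 − u). In the HMA-failure cohort, with true toxicity 50% and true ORR 20%, exact calculation with looks at 5, 10 and 15 patients gives these early-stop probabilities:

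| u | Recorded rate | P(stop early) |
|---|---|---|
| 0 | 0.500 | 0.606 (Table 10: 0.6062) |
| 5% | 0.475 | 0.540 |
| 10% | 0.450 | 0.474 |
| 20% | 0.400 | 0.352 |

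This shows the rule's sensitivity to missed events. It does not estimate how many are missed.

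**The case against.** A reader might infer that recording simply stops at day 30. The documents do not support so clean a rule, because the looser wording in 7.1.2.1 and the closing words of the 7.2 sentence leave later recording open. What stands is a conflict: three sections point to about day 30, two phrases point beyond it, and none assigns the later questioning.

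A reader might also count three incompatible SAE windows. Section 5.8 gives 90 days but refers to 7.2.3.1 for the detail, so it is not an independent rule. Two rules conflict, and only for patients starting new therapy within 90 days. Even then, for a start before day 30, the all-AE sentence in 7.2 and the SAE rule in 7.2.3.1 both still require capture to day 30.

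Nor does it follow that late immune toxicity as a whole is under-counted. Related SAEs are reportable at any time, important medical events may be classed as serious, and hospitalization is itself a seriousness criterion, so many related grade 3 immune events would plausibly be reported. AEs above grade 1 already present at the safety visit are followed to grade 0-1 or new therapy. Grade 2 events never enter Tables 8 and 11.

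Finally, the 5/10 versus 6/10 contrast holds for any missed patient, whatever the cause. It applies here only if someone already more than 30 days off treatment at that look has a first qualifying event that is not serious. Section 8.1 states no observation window, so it is an inference that the 7.2 window governs the toxicity count. These limits narrow the point but do not remove it.

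**Conclusion.** The concern holds in a limited form. The AE sections conflict on whether non-serious events are recorded after about day 30, and the protocol's own statement about timing makes that period relevant. The exposed group is new-onset, non-serious grade 2-3 immune events after day 30 that fall outside the liver-test threshold. The SAE cut-off also differs between 7.1.5.3.1 and 7.2.3.1 for new therapy starting within 90 days, by 20 days for a start on day 10 (10 versus 30) and by 15 days for a start on day 45 (45 versus 30).

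The size of any under-count is unknown. The stopping-rule figures show that one patient can decide continuation, but not that this is likely. A reader might infer that different sites would report differently; the documents describe treatment at one institution, so the sounder statement is that two readers of the same text could differ. The correction is worth making because it bears on a primary objective and costs little.

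**What to change.** 1. **AE window.** Record immune-mediated AEs of the Table 3 types, grade 2 or higher and serious or not, to 90 days after the last pembrolizumab dose, whether or not new therapy starts, and note the date of any new therapy so that attribution can be judged. Ordinary AE records are enough. Adding these types to the events-of-clinical-interest list would trigger 24-hour sponsor reporting, which this purpose does not need. Align 7.1.2.1 and 7.2 with this window. Ninety days matches the SAE period already in the protocol; it may still miss the latest of the events that 5.2.1.2 describes.
2. **SAE window.** State one identical rule in 5.8, 7.1.5.3.1 and 7.2.3.1, including what happens when new therapy starts.
3. **Toxicity endpoint.** State in 8.1 the period over which grade 3/4 toxicity counts toward Tables 8 and 11.

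**Cost.** A wording amendment, a few more AE records (some confounded by the next therapy), and an AE question at contacts that already exist, including calls now specified only for survival status. No dose or treatment rule changes.
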